- After recruitment, participant experiences surgical complications (bladder or bowel injury, etc) that require face-to-face postoperative care
- After recruitment, participant visits the emergency room (ER) for postoperative complaints between surgery and scheduled postoperative visit

Materials and Methods

Study design: Randomized controlled trial.

Once IRB approval is obtained, we will begin recruitment based on the stated inclusion and exclusion criteria. Invitation to participate will be extended to eligible patients by clinic staff with a direct care relationship to the patient during their pre-operative visit in the TTUHSC El Paso Ob-Gyn department. If the patient agrees to participate, research staff will be called in to explain the study in more detail. The patients will be advised that if they agree to enroll, there is a 50% chance their post-operative visit may be via tele-medicine and 50% chance it will be as a traditional visit in the office. They will be asked to fill out a short survey that verifies they have a compatible mobile phone, and will be asked to download the appropriate app. An instruction sheet on how to utilize the tele-medicine application will be given to all patients, to be used in case they are allocated to the tele-medicine group. Once enrolled, surgery will proceed as planned. After surgical stop-time, patients will be allocated to either a traditional postoperative visit group or a tele-medicine postoperative visit via block-randomization, utilizing block sizes of 4:6. This will be achieved by giving patients a sealed envelope that allocates them in a sequential fashion based on a previously generated random series. The envelope will contain information regarding group assignment, along with simple instructions as to how to schedule the post-operative visit within a window between one and three weeks from the surgery.

Both the tele-medicine and traditional visits will be carried out using the same structure.

- 1) Inquire about any concerns the patient has regarding recovery.
- 2) Review findings and procedures done during surgery and pathology results.
- 3) Visually examine abdominal laparoscopic port-sites.
- 4) The opportunity for the patient to ask any additional questions.

In the case of the telemedicine visits, they will open by asking the patient to state her full name, and her date of birth. Additionally, this will be correlated with the code in the instruction sheet in order to verify identity.

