Our primary outcome is to detect a difference in patient satisfaction. If we expect a 20% relative increase in the experimental arm, assuming two-tailed testing with an alpha of 0.05, and power of 80%, we will need a total sample size of 64 patients. This is considering a base satisfaction score of 70, with a standard deviation of 20.

Safety Procedures:

-Confidentiality and Privacy: Data will be stored in a secure de-identified database. No personal/identifiable information will be collected in this database. A separate list that contains a list of enrolled patients, with information including patient name, phone number and internal research code will also be generated for the purpose of performing the follow-up surveys. The information from the surveys will then be uploaded into the de-identified database by using the internal research code.-Safety – A member of the research staff will be assigned as a safety monitor. Interval analysis will be performed for every 20 patients recruited. If the experimental arm demonstrates an increase of greater than 10% in visits to the emergency-room related to post-operative complaints, or an increase in unexpected complications (wound infection, wound dehiscence, etc.), the study will be halted. However, only patient's undergoing minimally invasive surgery will be included, which is known to have a lower wound-related complication rate than traditional surgery, so we do not expect any significant difference regarding complications.

Data Management:

All data will be collected in a de-identified fashion and stored on Redcap, which is approved TTUHSC IT software. Only approved members of the research team will be granted access. The data will be stored in a secured server. Data will not be linked by code to any identifying information.

Data analysis:

All data analysis will be carried out in SPSS version 24 (IBM, Armonk, NY, USA). We will use T-student to compare demographic variables that are continuous (age, BMI), as well as duration of the visit and number of readmissions or phone-calls. Pearson's Chi Square will be used when analyzing categorical binary variables.

Strengths/limitations

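### Few-event clinical outcomes have no planned interval and no suitable method; the t-test named for readmissions can be non-computable or give a misleadingly narrow interval

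*Combined protocol and SAP*

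**What the plan says.** The Data analysis section gives Student's t-test to continuous demographic variables "as well as duration of the visit and number of readmissions or phone-calls". For the rest, "Pearson's Chi Square will be used when analyzing categorical binary variables". It names no exact test, no rule for small expected counts, no count method and no confidence interval for any outcome.

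The Sample size section reads: "assuming two-tailed testing with an alpha of 0.05, and power of 80%, we will need a total sample size of 64 patients". Materials and Methods tells patients that "there is a 50% chance their post-operative visit may be via tele-medicine and 50% chance it will be as a traditional visit", so about 32 per arm.

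Objective 3 is to look for differences in surgery-related ED visits and delayed complications. The Hypothesis section expects none in ED visits or unrecognised complications. Materials and Methods collects phone calls and ED visits after the postoperative visit, up to day 30 after surgery. Readmissions are named only in the Data analysis sentence.

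No event rate is given for any clinical outcome. The nearest statement is in Safety Procedures, which says of minimally invasive surgery "which is known to have a lower wound-related complication rate than traditional surgery". That is comparative, and about wounds only.

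**The concern.** Several features suggest that events will be few. Patients with an emergency room visit before the postoperative visit, or with a surgical complication needing face-to-face care, leave the study. Events then count only from a visit held one to three weeks after surgery until day 30.

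If most patients score 0 for readmission, a t-test compares two nearly constant samples. With no events at all, both variances are zero and the test does not exist. With one or two events, all the variance comes from those patients, and the empty arm adds no uncertainty to the interval.

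Objective 3 is framed as no difference. A non-significant or missing p-value cannot show how large a difference 64 patients leave open; only an interval can. Results with very few events are the ones most likely to be read as reassuring. Safety Procedures treats an increase above 10% in ED visits as grounds to halt. Taken as percentage points (an assumption, since the text does not say), that is a natural yardstick for the interval.

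**Working it through.** **Inputs.** Two-sided alpha 0.05, total 64 and 1:1 allocation are from the protocol. Event rates are assumed.

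**The plan's own figure.** From "If we expect a 20% relative increase in the experimental arm" and "This is considering a base satisfaction score of 70, with a standard deviation of 20", the difference is 0.20 × 70 = 14 points with SD 20. Per arm: 2 × 20² × (1.960 + 0.842)² / 14² = 32.04. The stated 64 is reproduced to within rounding (strictly 33 per arm, 66 in all; power at 32 per arm is 79.96%). This sizes satisfaction only. For the clinical outcomes it just fixes 32 per arm, before any removals.

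**When the t-test cannot be computed.** With the same rate p in both arms, P(no events in either arm) = (1 − p)^64.

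| Assumed rate per arm | P(no events) |
|---|---|
| 1% | 52.6% |
| 2% | 27.4% |
| 3% | 14.2% |
| 5% | 3.8% |
| 10% | 0.1% |

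**Interval with 1 event against 0.** The difference is 1/32 = 3.125 points.
- t interval: the arm variances are (1/32)(31/32)(32/31) = 0.03125 and 0, so the pooled variance is 0.015625. SE = √(0.015625 × 2/32) = 0.03125. With t(62 df) = 1.999, the interval is 3.125 ± 6.25, that is -3.1 to +9.4 points.
- Newcombe: the Wilson limits are 0.55% to 15.74% for 1/32 and 0% to 10.72% for 0/32. Lower limit: 3.125 − √((3.125 − 0.55)² + 10.72²) = -7.9. Upper limit: 3.125 + (15.74 − 3.125) = +15.7.

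The t interval stops short of +10 points; Newcombe's does not. With 0 against 0 the t formula gives zero width and Newcombe gives ±10.7 points.

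**Coverage of a nominal 95% interval**, by exact enumeration of two Binomial(32, p) arms:

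| True rates | t, all samples | t, 0-0 samples dropped | Newcombe |
|---|---|---|---|
| 1% vs 3% | 72.3% | 99.5% | 99.96% |
| 1% vs 5% | 80.3% | 93.4% | 99.6% |
| 2% vs 5% | 87.0% | 96.8% | 99.2% |
| 3% vs 6% | 90.8% | 95.8% | 98.5% |

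At equal rates, counting a zero-width interval at 0 as covering, the t interval covers 99.6% (2%), 96.8% (5%) and 94.4% (10%). Its lowest value over rates up to 50% is 94.0%.

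**Pearson's chi-square.** The expected event count per arm is half the total, so it is below 5 whenever there are 9 or fewer events in all. That happens in 99.9% of trials at 5% per arm, 89.7% at 10% and 50.3% at 15%. The type I error is nevertheless 0.4% at 2%, 3.2% at 5%, 5.6% at 10% and 5.1% at 20%, and peaks at 6.0% over rates up to 50%.

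**A borderline table, 4 against 0.** Pearson p = 0.039, t-test 0.039, Barnard 0.045, Boschloo 0.068, Fisher 0.113. Barnard and Boschloo are computed with the 32 per arm held fixed. The two unconditional exact tests fall on opposite sides of 0.05.

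**Phone calls.** For simulated Poisson and overdispersed counts with equal means of 0.1 to 1 per patient, the t-test's type I error was about 4% to 5%.

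**The case against.** The strongest reply is that the plan contains no interval, so nothing in it can have the wrong width. That is correct. A reader might infer that the plan's error bars are wrong; it has none. The gap is that no interval is specified, and the one that accompanies the named t-test is a poor substitute when events are few.

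A reader might also infer that the t-test will often fail, or that its interval generally covers well below 95%. The documents support neither. Frequent failure needs rates of about 2% or less, and no rate is given. The low coverage figures arise only when rates are very low and truly unequal, and mostly restate the 0-0 case. Under the protocol's own hypothesis of equal rates, coverage is 94% or more.

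Nor are the planned tests invalid. Failure of the expected-count rule does little harm to chi-square's error rate here, and the 4 against 0 table does not show exact methods uniformly overturning it, since Barnard stays below 0.05.

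Finally, Methods can be read as recording whether there was any ED visit, which would fall under chi-square rather than the t-test. That narrows the t-test problem to readmissions, which Methods does not list as collected. It leaves the missing interval untouched.

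**Conclusion.** The point holds in limited form and is minor. The plan names a t-test for readmissions and chi-square for binary outcomes at about 32 per arm, with no interval and no method for few events, so Objective 3 would rest on a non-significant or non-computable test. If events are rare, the t-test fails in 53%, 27% or 4% of trials at 1%, 2% or 5% per arm. With a single event, its interval appears to rule out a 10-point increase that Newcombe's leaves open up to 15.7 points.

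This rests on assumed rates, on 32 analysed per arm (removals would lower that), and on reading the safety threshold as percentage points. The false-positive rate, the comparison of phone calls at the means tried, and the satisfaction outcome with its sample size are not called into question.

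**What to change.** In Data analysis:

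- Analyse ED visit as any versus none per patient. Do the same for readmission if it is collected; otherwise remove the word. If it stays, define it in Materials and Methods.
- Report the risk difference with a Newcombe 95% interval as the main result for Objective 3.
- Name one exact unconditional test in advance, for example Boschloo's, for use when any expected cell is below 5. Leaving a choice between Boschloo and Barnard would allow either conclusion at 4 against 0. Fisher's test is very conservative at this size (type I error 0.2% at a 5% rate).
- Keep the t-test for visit duration. A permutation p-value for phone calls is optional.

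The cost is a wording change, somewhat wider intervals, and a few lines of code outside SPSS, so the sentence placing all analysis in SPSS 24 needs a matching edit. The sample size does not change.
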